#### 9.4.1.4. End of study questionnaire

An end of study visit will be completed by the participating doctor for all patients who discontinued the study before 36 months follow-up planned by the protocol (patient lost to follow-up, patient died or patient who withdrew their consent).

#### 9.4.1.5. Measurement of compliance with treatment

Compliance with treatment will be evaluated directly in patients using a Morisky standardized validated questionnaire (Annex 3). This generic questionnaire on evaluation of adherence with treatment consists of 7 questions for which the rating scale is 0 for “YES”

(reflection of poor compliance) and 1 for “NO” (reflection of good compliance), and an 8th question with 5 response modalities ranging from “never/rarely” to “all of the time” which makes it possible to qualify the degree of agreement [23].

This questionnaire will be returned by the patient to the participating doctor at the end of the visit. All adverse events identified by the participating doctor via these questionnaires (if the patient has ticked YES to questions **3, 6**) must be reported in the study database and be reported through the Pfizer Pharmacovigilance department (*see section 11 Erreur ! Source du renvoi introuvable.*

#### **9.4.1.6. Measurement of quality of life**

Patient quality of life depends on treatments received and on complications encountered. It will be measured at the inclusion visit and at certain follow-up visits (M3, M6, M12, M18, M24, M36), by completion of a standardized questionnaire and validated in French FACT-leu (Functional Assessment of Cancer-Therapy-Leukemia, version 4 November 2007) in paper format for all patients in the study (Annex 3).

The FACT-leu questionnaire is a 44-item questionnaire with 5 modalities ranging from 0 (“not at all”) to 4 (“enormously”), evaluating 5 major dimensions of quality of life in the last 7 days: physical well-being (7 questions, score of 0 to 28), social/familial well-being (7 questions, score of 0 to 28), emotional well-being (6 questions, score of 0 to 24), functional well-being (7 questions, score of 0 to 28), and other subjects of concern (17 specific questions on leukemia, score of 0 to 68). A total score (of 0 to 176) can be calculated; a high score reflects good quality of life [24].

This questionnaire will be returned by the patient to the participating doctor at the end of the visit. All adverse events identified by the participating doctor via these questionnaire (e.g. “I have nausea” scored between 1 (a little) and 4 (enormously)) should be recorded in the study database and be reported to the Pfizer Pharmacovigilance department (*see 11 Erreur ! Source du renvoi introuvable.*

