### **9.7.3. Analyses of secondary objectives**

#### **Safety profile with bosutinib:**

- The following percent will be described by System Organ Class (SOC) overall and according to grade of event whether it is considered as related to bosutinib or not (grade 1, 2, 3, 4, or grades 3/4):
  - o percent of patients presenting with AE that occurred with bosutinib
  - o percent of patients presenting with AE which required a change to treatment with bosutinib (a reduction of dose and/or temporary or permanent discontinuation)

- The percent of patients presenting with biological or hematological toxicities during treatment with bosutinib, whether considered related to bosutinib or not, will be described overall and according to grade of the event (grade 1, 2, 3, 4, or grade 3/4).  
The biological and hematological events will be estimated by the CTCAE v4.03 criteria of June 2010, with all values greater than the upper normal value, or lower than the lower normal value of the parameter considered.
- Measures taken to prevent AE will be described (supportive therapy, etc.).
- Biochemical and hematological parameters will be described in follow-up using a linear mixed model for repeated data.

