## **11.5. Definition of an adverse event**

### **11.5.1. Adverse event**

An adverse event is any unwanted manifestation that occurred in a patient to whom a medicinal product was administered. It is not necessary for the event to have a causal relation with the treatment or use. Examples of adverse events include, without this list having a limited characteristic:

- Abnormal test results (see in the following for circumstances in which an abnormal test result is an AE);
- Clinically significant symptoms and signs;
- Changes to results of the clinical examination;
- Hypersensitivity;
- Lack of efficacy;
- Drug abuse;
- Medicinal product dependence.

Furthermore, for medicinal products, they can include resultant signs and symptoms of:

- an overdose;
- withdrawal;
- misuse;
- off-label use;
- drug interaction;
- extravasation;
- exposure during pregnancy;
- exposure during lactation;
- a medicinal product error;
- occupational exposure.

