**Annex 3.3: Morisky 8-item questionnaire on adherence to treatment**

**Questionnaire in relation to your treatment**

(Mark only one response per question)

	Yes	No
1. Do you ever forget to take your treatment?		
2. Sometimes some persons do not take their medicinal products for reasons other than forgetfulness. By thinking about the last two weeks, have there been any days when you did not take your treatment?		
3. Has it ever happened for you to reduce the dose or to discontinue taking your treatment without telling your doctor because you feel less well by taking it?		
4. When you travel or when you leave the house, does it happen that you forget to take your treatment with you?		
5. Have you taken your treatment yesterday?		
6. When you experience much less or even not at all your symptoms, does it happen sometimes for you to stop taking your treatment?		
7. Does the fact of having to take your treatment everyday represent a real inconvenience for certain patients? The fact of having to take your treatment every day represents a real inconvenience for certain patients. Does it sometimes happen for each to be upset by the fact of having to adhere to your treatment?		
8. Does it happen that you have difficulty in remembering to take your treatment?  Never/Rarely  From time to time  Sometimes  Regularly  All the time		

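### Questionnaire-identified symptoms can be recorded as adverse events on bosutinib without being new or worse since the first dose, and a Yes to Morisky item 6 is an AE trigger although it reports non-adherence

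*Protocol*

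**What the plan says.** Section 9.4.1.6 opens its reporting rule with "All adverse events identified by the participating doctor via these questionnaire" and illustrates it with the nausea item, "scored between 1 (a little) and 4 (enormously)) should be recorded in the study database". No other item is named, and no comparison with an earlier score is asked for. Section 9.4.1 and Table 4 place FACT-leu at M0 and at M3, M6, M12, M18, M24 and M36, for patients on bosutinib.

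Section 9.4.1.5 has a parallel rule for the adherence questionnaire: "All adverse events identified by the participating doctor via these questionnaires (if the patient has ticked YES to questions" 3 and 6. These events "must be reported in the study database and be reported through the Pfizer Pharmacovigilance department". In Annex 3.3, item 6 reads "When you experience much less or even not at all your symptoms, does it happen sometimes for you to stop taking your treatment".

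Section 11.5.1 defines the event broadly: "An adverse event is any unwanted manifestation that occurred in a patient to whom a medicinal product was administered". It sets no condition of onset or worsening after the first dose. Under Table 5 in section 11.2, all AEs go into the eCRF whatever their relation to bosutinib. Section 9.7.3 then reports the "percent of patients presenting with AE that occurred with bosutinib", whether related or not. The primary percentages in section 9.7.2 count only AEs that the doctor considers related.

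**The concern.** Patients enter because they are resistant or intolerant to an earlier TKI, so some will plausibly bring symptoms with them. Suppose a patient scores nausea 2 at M0, before the first dose, and 1 at M3. The symptom has improved, yet the M3 score falls within the range that section 9.4.1.6 gives as its example of an AE. Another patient with the same low score at M0, M3 and M6 is unchanged and falls within it too. Nausea is also among the most common AEs that section 7.3 reports for bosutinib, so carry-over would fall on an event of direct interest.

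Morisky item 6 raises a different problem. A Yes says that the patient stops treatment when feeling better. That is adherence information, which the study already analyses separately, and it describes no symptom.

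At stake is what the all-AE percentages mean. If they mix events that arose on bosutinib with symptoms that preceded it, they overstate the former, and a larger sample would not remove the excess.

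**Working it through.** **The texts side by side.** The protocol applies a filter elsewhere that it does not apply here.
- Section 11.5.1 lists symptoms and signs of clinical significance among its AE examples; the example in 9.4.1.6 starts at the lowest non-zero answer.
- For abnormal tests, the same section sets four criteria for when a result is to be reported as an AE. Questionnaire symptoms have none.
- In section 11.5.2, the hospitalization text separates admission for a pre-existing disorder from a new AE or a worsening. The idea is present but is not carried over to symptoms.
- Morisky item 3 asks whether the patient has reduced the dose or had to "discontinue taking your treatment without telling your doctor because you feel less well by taking it". That can point to an unwanted manifestation. Item 6 asks about stopping when symptoms are reduced or absent and does not meet the definition in 11.5.1.

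**The plan's own precision figure.** Section 9.5 gives a half-width of at most 10% for about 100 patients (Wald, 50% rate, 95% interval): 1.96 × √(0.5 × 0.5 / 100) = 0.098, or 9.8 points. The figure is reproduced.

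**Size of the possible excess.** The documents give no symptom prevalence, so the inputs below are assumptions:
- p: true percentage of patients with an AE arising on bosutinib, set at 50% to match section 9.5;
- b: percentage with a persisting pre-bosutinib symptom scored 1 or more, taken as 10%, 30% and 50%;
- f: share of these that the doctor records as an AE, taken as 0.25, 0.5 and 1;
- independence between the two sources.

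Counted percentage = 1 − (1 − p)(1 − b·f), so excess = (1 − p)·b·f. Example: b = 30%, f = 1 gives 0.5 × 0.30 × 1 = 15 points, and 65% is counted instead of 50%.

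| b | f = 0.25 | f = 0.5 | f = 1 |
|---|---|---|---|
| 10% | +1.25 | +2.5 | +5 |
| 30% | +3.75 | +7.5 | +15 |
| 50% | +6.25 | +12.5 | +25 |

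The excess passes 9.8 points when 0.5·b·f > 0.098, that is, when b·f exceeds 0.196. In the table this happens at b = 30% with f = 1, and at b = 50% with f = 0.5 or 1. With an assumed p of 20%, the excess is 0.8·b·f and runs from +2 (b = 10%, f = 0.25) to +40 points (b = 50%, f = 1). Under a new-or-worse condition the carry-over excess is zero by construction.

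**The case against.** The strongest reply is that the doctor identifies the AE and that nausea is one example. A reader might infer that every FACT-leu answer of 1 or more automatically becomes an AE and that the percentages drift towards 100%. The text does not say that. Both questionnaire rules begin with the doctor's identification, and the doctor knows the comorbidities and the AEs on earlier TKIs. This stands, and it is why f is varied. What remains is that the only guidance given to about twenty centres is a threshold of 1, with no mention of baseline.

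One could also multiply over items: if an unaffected patient has a 5-20% chance of a non-zero answer per item, 30-79% would score on at least one of seven independent items. That does not measure carry-over. Many such answers would be new after M0, and the calculation assumes independent items and full recording.

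A second reply is that section 11.3 opens the reporting period at the first dose, or at consent if the patient is already exposed. That excludes a score given at M0 before the first dose. It does not clearly exclude the same symptom still present at M3. Patients who started bosutinib in the month before inclusion may have no pre-dose rating at all.

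A third is that treatment-emergence rules belong in the SAP, to which sections 9.7.2 and 9.7.3 leave the detail. An SAP could indeed set the counting rule. Sections 9.4.1.5 and 9.4.1.6, however, are capture instructions in the protocol, and an SAP does not change what doctors are told to enter.

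On item 6, a vigilance prompt has some basis, because Table 5 requires misuse and medicinal product errors to be reported with or without an AE. That is a separate line and does not make the answer an AE. Nor is item 6 about missed doses through forgetting: those are items 1 and 4, which are not triggers.

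**Conclusion.** The point holds as a defect in the capture instructions and should be corrected. The documents let a symptom carried over from before bosutinib be recorded as an AE on bosutinib, and they name a non-adherence answer as an AE trigger.

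The main effect is on the secondary all-AE percentages in section 9.7.3. At an assumed true 50%, with 10-50% of patients having persisting symptoms, the excess is about +1 to +6 points if doctors record a quarter of them and +5 to +25 if they record all. It exceeds the 9.8-point half-width only where persisting symptoms are common and at least half are recorded. All these figures rest on assumed prevalence and recording, and on independence.

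A reader might infer that the primary related-AE percentage is distorted to the same degree. The documents do not support this: section 9.7.2 counts only events that the doctor considers related, and section 11.4 bases that on a reasonable possibility that bosutinib caused or contributed to the event. Some leakage is possible because contribution suffices, but the effect should be smaller. The discontinuation endpoint also requires permanent stopping. Results by grade limit the damage further, since mild carried-over symptoms would not be expected among grade 3/4 events.

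**What to change.** Leave pharmacovigilance reporting as it is. In sections 9.4.1.6 and 9.7.2/9.7.3, state that a symptom identified through a questionnaire counts in the AE percentages only if the doctor records it as new or worse since the first bosutinib dose. Use the M0 rating as the comparison where M0 precedes the first dose, and the doctor's onset date otherwise.

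In section 9.4.1.5, remove item 6 as an AE trigger. Alternatively, record a Yes as non-adherence, and under the separate misuse line of Table 5 where that applies, without counting it as an AE.

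The cost is a few sentences plus an eCRF flag for AEs identified from questionnaires. The flag is needed because section 9.6.1.1 has AEs entered in the eCRF while the paper questionnaires are entered separately by the CRO. The remaining weakness is that patients without a pre-dose rating depend on the doctor's onset date.

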#### **9.4.1.7. Registry of non-inclusion:**

Patients eligible but not included must be recorded in a non-inclusion registry (*see ANNEX 3.7: Registry of non-inclusion*), with a minimum of parameters collected:

- Demographic characteristics (year of birth, gender),
- Reason for non-inclusion.

## **9.5. Study sample size**

Since the descriptive objective of this study does not involve the hypothesis of specific research, it is not necessary to calculate a minimum sample size population of participating

patients. Furthermore, since CML is a rare disease, a minimum number of patients is not expected.

Based on the number of monthly prescriptions of Bosulif® (sponsor data) and taking into account the future start-up of a competitive study, a total of one hundred (100) patients included in the study appears to be a reasonable objective. Participating doctors should include on average 5 patients in the study, with no distinction between phases of CML at inclusion.

However, it is shown that about one hundred patients would make it possible to have acceptable precision, precision corresponding to half of a 95% confidence interval (CI):

- $\leq 10\%$  to estimate a percent of patients presenting with a given event (Wald asymptotic method without a continuity correction – hypothesis of a 50% rate)
- Of 10% in order to estimate median survival (Greenwood formula under the hypothesis of absence of data censored at the right before median survival and occurrence of a single event at a time).

Consecutive inclusion of patients who satisfy eligibility criteria up to the end of the inclusion period estimated at 2 years will ensure the representativeness of patients in the study.

In order to ensure compliance with this consecutiveness, a registry of non-inclusion will be set up. Patients eligible but not included in the study must be recorded in this registry and throughout the period of inclusion. A minimum of parameters will be collected.

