
NATURE AND DURATION OF STUDY
	
This is a national, observational, descriptive, prospective, multi-centre study conducted in Metropolitan France in adult patients treated for chronic phase, accelerated or blast phase Philadelphia chromosome positive (Ph+/-) CML, previously treated with one or more TKIs and for whom imatinib, dasatinib or nilotinib are not considered as appropriate treatments. The study will be conducted in all centres involved in management of CML, i.e. about twenty (20) centres are expected.
 
The study will be offered to all patients who satisfy criteria for eligibility up to the end of the recruitment period. Eligible patients but not included in the study will be recorded in a non-inclusion registry.
 
Patients will be followed prospectively throughout the duration of the study (3-year follow-up) starting from their inclusion in the study. Follow-up data will be collected at follow-up visits conducted in the setting of usual management, estimated at every 3 months independently of discontinuations, changes or discontinuations of treatment possibly implemented. Therapeutic management of the patient will not be

	
changed by participation in the study.

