### **9.7.2. Analysis of the primary objectives**

The following parameters will be evaluated in order to respond to the primary objectives:

- The percent of patients presenting with adverse events considered related to bosutinib by the participating doctor will be described overall (all grades of seriousness combined, all types of events combined), depending on grade: 1, 2, 3 and 4 and grades 3/4, and by type of event.
- The percent of patients who permanently discontinued treatment with bosutinib following an AE considered related to bosutinib by the participating doctor will be described overall.

Analysis of the primary objectives will be detailed in the statistical analysis plan.

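### The precision of 10% or less in section 9.5 holds only for independent patients, but the design takes about 5 patients per doctor from about 20 centres and the primary endpoints are doctor-judged

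*Protocol*

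**What the plan says.** Section 9.5 sets the target on feasibility grounds: "a total of one hundred (100) patients included in the study appears to be a reasonable objective". It then claims that about 100 patients give a 95% CI half-width of at most 10% "to estimate a percent of patients presenting with a given event", with the method given as "Wald asymptotic method without a continuity correction – hypothesis of a 50% rate". The same section adds: "Participating doctors should include on average 5 patients in the study". The synopsis says that "about twenty (20) centres are expected", and section 9.1 repeats the number.

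For the first primary objective, section 9.7.2 says: "The percent of patients presenting with adverse events considered related to bosutinib by the participating doctor will be described overall". The second is the percentage who permanently stop bosutinib after an event that the same doctor considers related. Section 11.4 makes causality the doctor's assessment, and section 9.1 leaves treatment and follow-up to the doctor.

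Section 9.7.1 plans a 95% CI for each frequency without naming a method. Section 9.7.2 leaves the detail of the primary analysis to the SAP. Neither 9.5 nor 9.7 mentions clustering by centre or doctor. The mixed models in 9.7.1 are for repeated continuous laboratory data, not for these proportions.

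**The concern.** The formula printed in 9.5 does not match the sample described in 9.5. A Wald variance at n = 100 assumes that each patient contributes independent information. Here one doctor elicits, attributes and acts on the events of about five patients. Doctors differ in how readily they call an event drug-related and in how soon they stop a drug, so patients of one doctor will tend to resemble each other on exactly these two outcomes. A zero ICC is possible but would be the special case.

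The protocol also treats its doctors as a sample from a wider group. Section 9.7.4 checks whether they represent hematologists in France, and section 9.9.1 describes voluntary recruitment. Variation between doctors therefore belongs in the uncertainty of an estimate meant for French practice. At stake is the claimed precision of both primary percentages, and their coverage if the formula of 9.5 is carried into the analysis. The point estimates are not affected.

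**Working it through.** **Inputs from the protocol.** N = 100, on average 5 patients per doctor, 50% rate and Wald interval (section 9.5); about 20 centres (synopsis and section 9.1). Since 20 × 5 = 100, the figures imply about one doctor per centre, so the cluster size is m = 5. As a second rate, section 7.3 reports that about 20% of patients in the earlier single-arm study stopped bosutinib after an AE. That covers any AE, so it is only a proxy for the second primary endpoint.

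**Assumed inputs.** The protocol gives no ICC and no spread of centre sizes. I use ICC 0.02, 0.05 and 0.10, with either equal centres or uneven centres of 1 to 16 patients (CV about 0.8).

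**1. The plan's own figure.** 1.96 × √(0.5 × 0.5 / 100) = 9.80 points. A half-width of exactly 10 points needs 1.96² × 0.25 / 0.10² = 96.04 independent patients. The figure is correct under its own assumptions, with 0.2 points to spare.

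**2. Allowing for clustering.** Design effect with equal centres: DE = 1 + (m − 1) × ICC = 1 + 4 × ICC. With uneven centres: DE = 1 + ((1 + CV²) × m − 1) × ICC = 1 + 7.2 × ICC at CV 0.8. The half-width is multiplied by √DE. At a 20% rate the starting value is 1.96 × √(0.2 × 0.8 / 100) = 7.84 points.

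| ICC (assumed) | Centres | DE | Effective N | Half-width at 50% | Half-width at 20% |
|---|---|---|---|---|---|
| 0.02 | equal | 1.08 | 93 | 10.2 | 8.2 |
| 0.05 | equal | 1.20 | 83 | 10.7 | 8.6 |
| 0.10 | equal | 1.40 | 71 | 11.6 | 9.3 |
| 0.02 | uneven | 1.144 | 87 | 10.5 | 8.4 |
| 0.05 | uneven | 1.36 | 74 | 11.4 | 9.1 |
| 0.10 | uneven | 1.72 | 58 | 12.9 | 10.3 |

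**3. Where the 10% bound fails.** The bound holds while DE ≤ (10 / half-width under independence)².
- At 50%: (10 / 9.80)² = 1.041. With equal centres, ICC = 0.041 / 4 ≈ 0.01.
- At 20%: (10 / 7.84)² = 1.627. With equal centres, ICC = 0.627 / 4 ≈ 0.16. With uneven centres, 0.627 / 7.2 ≈ 0.09.

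**4. Coverage if the Wald formula of 9.5 were used for the reported CI.** The large-sample approximation is 2Φ(1.96 / √DE) − 1. With equal centres it gives 94%, 93% and 90% at ICC 0.02, 0.05 and 0.10. A beta-binomial simulation (40,000 replicates, 20 centres, N = 100, 50% rate), which also captures the small-sample behaviour of the Wald interval, gives about 93%, 92% and 89% with equal centres. With uneven centres it gives about 93%, 90% and 85%.

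**5. Coverage of a centre-clustered interval** (robust variance with centre as cluster, t quantile on 19 degrees of freedom), same simulation at 50%: about 95% with equal centres and about 92% to 93% with uneven centres. It does better than Wald at each positive ICC tried. The gain is small at ICC 0.02 and clear at 0.10.

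**The case against.** **The analysis method is not fixed.** A reader might infer that the reported 95% CIs will be too narrow. The protocol does not support that. Wald appears only in 9.5 as a planning device, 9.7.1 names no CI method, and 9.7.2 defers the detail to a SAP that is not shown. The coverage figures are therefore conditional on carrying the 9.5 formula into the analysis. The planning statement is different, because 9.5 prints both the method and the result.

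**Precision did not set N.** A reader might also infer that 100 patients are too few. Section 9.5 says that no minimum size needs calculating and bases the 100 on prescription volume and a competing study. The precision figure illustrates what that number delivers, so nothing here calls for more patients.

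**50% is the worst case.** This stands. Near a 20% rate there is ample room at modest ICCs. But 9.5 offers 10% as a general bound for any given event, and it is the general bound that fails.

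**The ICC and the uneven sizes are assumptions.** This also stands. It cannot be stated as fact that the effective N is below 100, only that it is for any positive ICC. With equal centres and ICC up to 0.05 the loss is under one point.

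**The study invites all CML centres and enrols consecutively.** If nearly all such centres took part, between-centre variation would be largely a feature of the population, not sampling error, and the figures above would overstate it. Participation is voluntary, however, and the protocol plans to test whether the doctors are representative. This softens the size of the point but does not remove it.

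**Conclusion.** The point holds in conditional form. The 10% in 9.5 is computed correctly, but for independent patients, and the protocol describes about 20 clusters of about 5 with doctor-judged primary endpoints. Over an assumed ICC of 0.02 to 0.10, the half-width at 50% is about 10.2 to 11.6 points with equal centres and about 10.5 to 13 with uneven ones. At a 20% rate the bound survives over that range with equal centres; with uneven centres it fails only near the top. Should the primary CIs be computed as in 9.5, coverage at 50% would run from about 93% down to 89% (equal) or 85% (uneven). This is a cheap improvement to the precision statement and the interval method.

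**What to change.** In section 9.5, state that a half-width of 10% or less assumes independent patients, and give the half-width over a stated ICC range at both 50% and 20% rates. The table above would serve, with the ICC and centre-size spread labelled as assumptions.

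In sections 9.7.1 and 9.7.2 (or in the SAP, with a pointer from there), compute the 95% CI of the two primary percentages with centre as the cluster, for example a survey-type or GEE robust variance with a t quantile on centres minus 1. Report the observed ICC or design effect next to each percentage.

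Cost: a few lines of wording and code. No new data are needed, because section 9.3 already makes the centre number part of the patient identifier, and enrolment does not change. The intervals become slightly wider and the advertised precision less favourable. With about 20 uneven centres the clustered interval still falls a little short of nominal, at about 92% to 93%.
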